3.2 Study Outcome Measures

3.2.1 *Primary*

Patient satisfaction with the partnered intervention components, based on exit interviews.

3.2.2 *Secondary*

Table 1 reflects the series of secondary outcome measures associated with the objectives of the study (i.e., the feasibility and acceptability of the partnered intervention).

Table 1. List of secondary outcome measures, with their corresponding constructs, levels of analysis, and data sources.

--

Constructs	Levels of Analysis	Measures (Quantitative / Qualitative)	Data Sources
IMPLEMENTATION OUTCOME MEASURES			
Acceptability	Provider	satisfaction with the partnering components and perceived ease of use of the remote entry EHR	exit interviews with patients; semi-structured interviews
Adoption	Provider Institution	uptake and utilization of remote entry EHR and partnering components by providers and program	observation; semi-structured interviews; EHR
Costs	Institution	intervention and implementation costs, including investment, supply, and opportunity costs	semi-structured interviews; EHR
Feasibility	Provider Site	extent to which the remote EHR entry and partnered intervention model are compatible with resources and training	semi-structured interviews; EHR
Fidelity	Provider	adherence to program protocol and quality of delivery	CHW logs; self-report
Sustainability	Institution Site	sustained remote EHR use at outreach events and partnering package of interventions	semi-structured interviews; EHR
SERVICE OUTCOME MEASURES			
Equity	Community Provider Family Patient	support from community partners, providers (including NYU Dentistry), family members & patients to direct resources to less well-served and less well-studied populations (Chinese American adults)	baseline survey; follow-up patient interviews; semi-structured interviews; EHR
ORGANIZATIONAL CHARACTERISTICS			
Engagement	Institution Site	commitment, involvement & accountability of leaders with the implementation	semi-structured interviews

- Work flow analysis of the interviews of research staff, NYU administrators, and providers (dentists and CHWs) is a secondary measure designed to evaluate and refine the use of the remote EHR.

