 - CHW Initial Intervention: Trained CHWs will deliver a culturally-tailored and language-specific oral health promotion program focusing on demonstrations with role-playing of proper brushing with fluoride toothpaste and flossing techniques. They will also provide culturally customized literature to the patients.
 - Acceptability Data Collection: Research staff will conduct a brief exit interview with each interview patient participant regarding acceptability of
-

the intervention and self-efficacy around oral health behaviors, requesting permission to contact her/his regular dental provider regarding receipt of a follow-up dental visit and providing a voucher worth \$205.00 for oral health care at NYU Dentistry to cover her/his comprehensive oral examination, treatment plan, and prophylaxis at no charge and with no co-payment required. The questions for this survey will be based on our previous oral health promotion program in the Sikh American community to assess acceptability. Prior to finalizing the survey for distribution to the interview patient participants, CAB members and research staff will adapt the questions as deemed appropriate for the Chinese American community and to be consistent with the ADA guidance on brushing with fluoride toothpaste.

- Feasibility Data Collection: We will also develop a checklist of 10 key components based on process (e.g., patient engagement) and the curriculum (e.g., topics covered) and ask if each one was covered. Endorsement of 8 of the 10 checklist items (80%) by the non-patient participants will be considered as the bar for success for feasibility. Finally, we will allow for open-ended collection of feedback on the feasibility of each of the partnered program components.

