7.4 Post-intervention Activities

- Feasibility and Acceptability Data Collection: Semi-structured interviews with participating dentists, CHWs, and other non-patient participants will be conducted (see section 8.1.3)
 - Feasibility Data Collection: EHR data will be reviewed to assess feasibility
-

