8.1.3 Semi-structured interviews regarding the remote EHR and partnered intervention

Semi-structured interviews will be conducted with participating dentists, CHWs and other non-patient participants in administrative and technical roles after the intervention. We anticipate conducting approximately 20 interviews before obtaining data saturation. The interviews will be informed by the Consolidated Framework for Implementation Research (CFIR) and Implementation Outcomes Framework (IOF) constructs and will assess specific barriers to sustaining the partnered intervention and strategies for addressing those barriers to facilitate integration of the intervention into the routine workflow of the NYU Dentistry Local Community Outreach Programs.

In addition to survey questions, acceptability will also be assessed using open-ended questions, such as:

- Please tell us what you liked most about the program.
 - Please tell us what you did not like about the program.
 - Please tell us what changes can be made to improve the program.
 - Overall program satisfaction (scale of 1-10 answer range)
 - How did you feel about the topics covered?
-

- How did you feel about the length of time of the dental screening and oral health promotion demonstrations?

Feasibility will be assessed among the dentists, CHWs, NYU administrators, and site directors at the 3 partnering organizations. The following questions will be asked:

- How did you feel about the intake procedures?
- How did you feel about the oral health demonstrations by CHWs?
- How did you feel about the length of time of each dental screening?

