12.2 Sample Size Considerations

No formal sample size estimates were performed for this F & A study. The bar for success for both feasibility and acceptability is 80% of enrolled patient participants report being satisfied or very satisfied with the partnered intervention components.

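### Neither feasibility success bar measures feasibility as Table 1 defines it: the 8-of-10 checklist in Section 7.2 measures fidelity, and the bar in Section 12.2 measures patient satisfaction

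*Combined protocol and SAP*

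**What the plan says.** Section 7.2, under Feasibility Data Collection, says the team will draw up the following instrument: "checklist of 10 key components based on process (e.g., patient engagement) and the curriculum (e.g., topics covered) and ask if each one was covered". The decision rule follows: "Endorsement of 8 of the 10 checklist items (80%) by the non-patient participants will be considered as the bar for success for feasibility". The ten items are not listed.

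Table 1 (Section 3.2.2) keeps two constructs apart. Feasibility is the "extent to which the remote EHR entry and partnered intervention model are compatible with resources and training", with semi-structured interviews and the EHR as sources. Fidelity is "adherence to program protocol and quality of delivery", with CHW logs and self-report as sources.

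Section 12.2 gives a second rule: "The bar for success for both feasibility and acceptability is 80% of enrolled patient participants report being satisfied or very satisfied" with the intervention components.

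Other feasibility information is planned:
- Section 7.2: "we will allow for open-ended collection of feedback on the feasibility of each of the partnered program components".
- Section 7.3: the CHW follow-up contact is labelled feasibility data.
- Section 7.4: "EHR data will be reviewed to assess feasibility".
- Sections 8.1.1 and 8.1.2: a workflow analysis, pilot testing and live usability observation of the remote EHR.
- Section 8.1.3: interviews of dentists, CHWs, NYU administrators and site directors. The listed feasibility questions concern intake, the CHW demonstrations, and "How did you feel about the length of time of each dental screening".

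Feasibility of remote EHR entry is also a secondary objective in its own right (Section 3.1).

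**The concern.** The study is meant to inform a larger randomized trial (Section 3). For that purpose a feasibility verdict should respond to the things that would stop the larger trial: records that cannot be entered on site, too few staff or too little space, or training that does not prepare people for the work. The checklist rule asks whether content was delivered. A program can deliver every topic while remote entry breaks down or the event strains the site, and a rule about coverage need not register either. The satisfaction rule does not close the gap, because patients can be content with a screening whose records never reached the EHR. The data that would show such problems are collected, but no stated rule turns them into a verdict.

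**Working it through.** **Step 1. Match each bar to its construct.**

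| Rule or row | What is asked | Who or what supplies it |
|---|---|---|
| Table 1, Feasibility | Fit of remote EHR entry and intervention with resources and training | Interviews, EHR |
| Table 1, Fidelity | Adherence and delivery quality | CHW logs, self-report |
| Section 7.2 bar | Was each process or curriculum component covered? | Non-patient participants |
| Section 12.2 bar | Is the patient satisfied or very satisfied? | Patient participants |

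In content, and in its reliance on staff report, the Section 7.2 bar lines up with the Fidelity row. The Section 12.2 bar lines up with neither row.

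**Step 2. Look for a metric or threshold in the other feasibility data.** Open-ended feedback (7.2): none. Follow-up contact (7.3): none. EHR review (7.4): none. Workflow and usability work (8.1.1, 8.1.2): formative, none. Interviews (8.1.3): open questions, none.

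**Step 3. Reproduce the plan's figure.** 8/10 = 0.80, which agrees with the stated 80%. The rule therefore tolerates 10 − 8 = 2 failed items.

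**Step 4. What can fail without missing the bar?** Let k be the number of the 10 items that concern resources, training or the EHR, and suppose all k fail. The bar is still met if at least 8 of the remaining 10 − k items are endorsed. Suppose each of those is endorsed independently with probability p:

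P(bar met) = P(X ≥ 8), where X ~ Binomial(10 − k, p).

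Example, k = 1 and p = 0.90: 0.90⁹ + 9 × 0.90⁸ × 0.10 = 0.387 + 0.387 = 0.775 after rounding.

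| k (all failed) | p = 0.80 | p = 0.90 | p = 0.95 | p = 1.00 |
|---|---|---|---|---|
| 0 (no such items) | 0.678 | 0.930 | 0.988 | 1.000 |
| 1 | 0.436 | 0.775 | 0.929 | 1.000 |
| 2 | 0.168 | 0.430 | 0.663 | 1.000 |
| 3 | 0 | 0 | 0 | 0 |

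With k = 0, such failures do not enter the count at all. With k = 1 or 2, they make a miss more likely but do not force it. With k = 3, at most 7 items remain and the bar must be missed.

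The documents give neither k nor p; both are assumptions. So is the reading of the rule as one yes/no result per item, because Section 7.2 does not say how endorsement is combined across raters or sites.

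**The case against.** The strongest reply is that the checklist has not been written. Its two examples are only examples, and the event process in Section 7.2 includes demographic entry, scanning and the dentist's direct entry, so an EHR item is plausible. This stands, and it limits the claim: a reader might infer that if EHR entry failed for half of the 150 patients the checklist would still read 10 of 10, but that assumes there is no EHR item, which the documents do not establish. What remains is that the text requires no such item, asks only about coverage, and tolerates two failures.

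Second, the study examines feasibility in several other ways. This also stands. A reader might infer that the study ignores EHR feasibility; it does not. A large entry failure should be visible in the EHR review planned in Section 7.4, and usability testing looks at workflow and educational needs. The gap is confined to the success rules.

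Third, the interview questions are not clearly silent on these matters. Intake is where information enters the EHR, the screening-length question touches on time burden, and the list is not said to be exhaustive. The documents therefore do not support a claim that the interviews miss the EHR or over-running events. But the listed questions do not name the EHR, and no answer affects a verdict.

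Fourth, a training failure might show up as topics not covered. That is partly right, so the point is strongest for resources and the remote EHR.

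Finally, Section 7.2 is not the only bar. Because Section 12.2 sets another under the same name, the documents do not show that the checklist alone would decide feasibility. This adds a need to reconcile the two; it does not supply the missing measure.

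**Conclusion.** The point holds as a mismatch between the plan's definition of feasibility and its two rules for declaring it. One rule measures fidelity and the other satisfaction. Unless three or more checklist items concern resources, training or the EHR, joint failure of all such items does not by itself cause the checklist bar to be missed. At an assumed endorsement probability of 0.90 for the other items, the bar would still be met with probability 0.775 (one such item) or 0.430 (two). These values illustrate the tolerance of the rule and do not forecast the study. The primary outcome, patient satisfaction from exit interviews, is unaffected. The correction is worth making because it is cheap while the checklist is unwritten, and because the feasibility verdict is meant to support a decision about a larger trial.

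**What to change.** 1. Report the 10-item checklist under Fidelity in Table 1 and Section 7.2.
2. Reconcile Sections 7.2 and 12.2 so that there is one feasibility bar, with patient satisfaction counting only for acceptability.
3. Base that bar on the EHR review already planned in Section 7.4: the share of EHR patient participants with demographics, scanned intake form and examination result all entered. Use the plan's own 80% level (0.80 × 150 = 120 patients) or another level fixed in advance. Entry failure for half of the patients (75/150 = 50%) would then miss the bar.
4. Add to the Section 8.1.3 interviews a rated question on fit with available resources, training and the remote EHR. Ask it of all the feasibility respondents named there: dentists, CHWs, NYU administrators and site directors (6 + 2 + 3 + 3 = 14 at the planned numbers). Report it alongside the EHR criterion. With 14 raters, one answer moves the share by about 7 percentage points (1/14), which argues against making it a second bar.
5. Report CHW follow-up contact within the Section 7.3 window descriptively. That contact is itself an intervention component, so making it a bar would again measure delivery. Do not require the walkout statement to be in the EHR, because the protocol does not say it is stored there.

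Cost: protocol wording, a small addition to the interviews and one EHR query. The downside for the sponsor is a feasibility verdict that can now fail on EHR completeness. The EHR share covers only the remote-entry part of the Table 1 definition; fit with resources and training rests on the rated question, which informs the verdict without deciding it.

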7.3 CHW Follow-up Contact with Interview Patient Participants (Feasibility Data Collection)

- CHW follow-up of oral health care receipt and dental hygiene behaviors will occur at approximately 1 month (window of -7 days to +1 month) after the partnered intervention. This contact may be via telephone or in person.
- Feasibility Data Collection: During this contact, the CHWs will assess whether or not each interview patient participant has received or has scheduled a dental visit. The CHWs will also inquire about use of fluoride toothpaste and frequency of teeth brushing since the last visit in a modified Oral Health Survey.
- If no visit has occurred or been scheduled, the CHW will offer to help schedule a dental visit for the interview patient participant or her/his family members at NYU Dentistry, her/his regular dentist, or one of the project-approved local oral health care providers.

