The partnered intervention consists of the following 4 evidence-based strategies: (1) written agreements of collaboration for dental screening at the site level; (2) culturally-tailored and language-specific adaptation of materials at the community and site levels; (3) demonstrations with role-playing of proper brushing with fluoride toothpaste and flossing techniques at the site and provider levels; and (4) community health worker (CHW) follow-up with patients about oral health care receipt and dental hygiene behaviors at the family and patient levels.

[figure not shown]
Patient Participants

Patient participants refer to study participants who are also patients screened at the urban outreach centers. Patient participants are first enrolled as EHR patient participants as part of the feasibility and acceptability study of this form of patient tracking. A subset of the EHR patient participants also complete exit interviews after the intervention at urban outreach centers and are referred to as interview patient participants.

Non-Patient
Participants

Non-patient participants refer to all other study participants who are not patients screened at the urban outreach centers, including community advisory board (CAB) members, research staff, New York University (NYU) administrators, providers (dentists and CHWs), and outreach site directors.

PROTOCOL SUMMARY

Title: Implementing a Participatory, Multi-level Intervention to Improve Asian American Health

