- Up to approximately 2 months (includes 1 in-person visit and 1 telephone follow-up) for each enrolled interview patient participant
- 1 day for each research staff member, NYU administrator, provider (dentist or CHW), CAB member or outreach site director to provide their input about factors affecting health care utilization among the clients of the outreach centers

Estimated Time to Complete Enrollment:

- Approximately 1 month to select the 3 participating outreach centers from the partners that have previously pledged their commitment to the study
 - Research staff, administrators, providers (dentists and CHWs) and clients/patients may be responding to feasibility and acceptability questions at any time during the study. Therefore, enrollment of these individuals can be open for the entire year of the study; participation in a particular set of questions can be completed in 1 day.
 - Enrollment of research staff, NYU administrators, providers (dentists and CHWs), CAB members and outreach site directors providing their knowledge about factors that influence access to oral health care and care-seeking behaviors among low-income, urban Chinese American adults can be open for the entire year of the study.
-

Schematic of Study Design:

¹May occur either before or after the start of the implementation of the partnered intervention

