7.2 Outreach Center Activities

- Health Insurance Portability and Accountability Act (HIPAA) certified research staff members or volunteers will explain the consent form, confidentiality agreement, and liability release to each potential patient participant and obtain her/his signature
- Remote EHR Data Collection and Dental Screening:

-
- Authorized NYU Dentistry personnel will directly enter the demographic information of patient participants into the customized EHR using the study-specific SCREENING option
 - EHR patient participants will complete a short paper intake form that will be scanned directly into a designated SCREENING folder in the EHR regarding medical conditions that could affect, or be affected by, their oral health (Yes / No checklist) and a brief questionnaire on self-reported receipt of a dental visit in the past year and dental hygiene behaviors (Oral Health Survey). These questions will be based on the World Health Organization (WHO) Oral Health Questionnaire for Adults: (1) How often do you clean your teeth? (Never, Once a month, 2-3 times a month, Once a week, 2-6 times a week, Once a day, Twice or more a day); (2) Do you use any of the following to clean your teeth? (Toothbrush, Wooden toothpicks, Plastic toothpicks, Thread (dental floss), Charcoal, Chewstick / miswak, Other (Please specify)); (3) For those who nominate Toothbrush: What type of toothbrush do you use? (Hard-bristled, Medium-bristled, Soft-bristled) (4) Do you use toothpaste to clean your teeth? (5) For those who nominate Toothpaste, Do you use a toothpaste that contains fluoride? Correct responses to all 5 questions will indicate that EHR patient participants are following the guidance of the American Dental Association (ADA) on brushing with fluoride toothpaste. These measures will be collected in person via self-report to ascertain baseline status at the beginning of each screening event and scanned directly into the NYU Dentistry remote EHR customized for community outreach events.
 - An NYU Dentistry faculty dentist will conduct a head and neck / oral examination on each EHR patient participant and directly enter the results into the customized EHR
- The dentist will review the examination results with the EHR patient participant using a customized walkout statement with screening results and follow-up notes and answer any questions regarding oral health concerns

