12.4 Final Analysis Plan

Acceptability of the partnered intervention will be assessed through exit interviews of the interview patient participants.

As we did with the Sikh American project, we will utilize a pre-post retrospective evaluation design. In this format, all questions will be asked in a single exit interview, but where applicable, will use the phrasing, "Prior to the beginning of the program..." followed by, "At the present time..." Table 3 lists the questions/domains we will use, and expected % changes we hypothesize we will observe in the current study. The percent change from pre-post will be compared using t-tests for proportions. Given that many of the answer choices are non-binary, we will also compare the shift of responses from pre-post across the categories of response using chi-squared tests. Note that this is not an exhaustive list of questions that will be asked; we are simply highlighting those questions that we will use to quantify acceptability. The full planned questionnaire is attached.

Health care utilization and oral health promotion measures: Our ultimate health care utilization measure of interest is receipt of a dental visit within the last 12 months. This will be measured using the Medical Expenditure Panel Survey (MEPS) definition, where dental visit refers to care by or visits to any type of dental provider. This will allow for

direct comparison with Healthy People 2020 Leading Health Indicator OH-7 to increase the proportion of children, adolescents, and adults who used the oral health care system in the past year.

Our central oral health promotion measure is self-reported brushing of teeth for 2 minutes twice a day with a soft-bristled toothbrush and fluoride toothpaste at the interview patient participant's 1 month follow-up visit. For the primary health care utilization measure of receipt of a dental visit within the last 12 months, we will also access the NYU Dentistry EHR database and follow-up with oral health care providers identified by participants in HIPAA approved procedures to ascertain receipt of a dental visit in the last 12 months.

Table 3 provides the measures and definitions of the oral health promotion, self-efficacy, and acceptability measures used in our prior research with the Sikh American community that will be adapted for the present F & A study with the Chinese American community.

Table 3. Measures and definitions of oral health promotion, self-efficacy, and acceptability measures

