Question/Domain	Observed Change in Sikh American Project	Expected Absolute Percent Change	Expected Relative Percent Change*
How often do you brush your teeth for at least two minutes?	Increase from 17.9% to 64.7% of those reporting "More than once a day"	+45%	+261%
How often do you floss?	Increase from 4.4% to 22.1% of those reporting "More than once a day"	+20%	+400%
How confident... a) are you that you know how to take good care of your mouth, teeth, and gums? b) do you feel asking your dentist or oral hygienist questions?	a) Increase from 0% to 65.7% of those reporting "Very confident" b) Increase from 7.4% to 75% of those reporting "Very confident"	a) +65% b) +65%	a) +6500% b) +864%
Agreement with the following statements: a) CHW answered my concerns and questions b) CHW helped me to improve how I take care of my health c) Information and topics were informative d) In-person demonstrations helpful in improving oral health	Reported "Strongly Agree" a) 57.4% b) 60.3% c) 69.1% d) 76.1%	N/A	N/A

**We additionally list relative percent change in the case that baseline behaviors among the Chinese American community are very different from the Sikh American community.*

The threshold for success for acceptability of the partnered intervention will be that 80% or more of interview patient participants rate all 4 acceptability questions as agree or strongly agree.

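### The hypothesised +20-point rise in flossing rests on a same-day exit answer; as described, no form records flossing frequency once patients have practised at home

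*Combined protocol and SAP*

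**What the plan says.** Section 7.2 describes the community health worker session as "demonstrations with role-playing of proper brushing with fluoride toothpaste and flossing techniques", so flossing is one of two skills taught. Table 3 in section 12.4 gives it a row of its own, "How often do you floss". The basis is the prior Sikh American project, "Increase from 4.4% to 22.1% of those reporting" flossing more than once a day, and the expected changes are +20% absolute and +400% relative.

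Section 12.4 collects the before and after answers together: "all questions will be asked in a single exit interview". The Special Terms section says that interview patients "complete exit interviews after the intervention at urban outreach centers". The Protocol Summary describes their participation as up to about 2 months and says that it "includes 1 in-person visit and 1 telephone follow-up".

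Two other forms touch on hygiene. The intake Oral Health Survey (7.2), completed at the start of the screening event, asks "Do you use any of the following to clean your teeth? (Toothbrush, Wooden toothpicks, Plastic toothpicks, Thread (dental floss" among other aids; its one frequency item concerns cleaning the teeth in general. The modified survey at about 1 month is described in 7.3: "The CHWs will also inquire about use of fluoride toothpaste and frequency of teeth brushing since the last visit in a modified Oral Health Survey". The central 1-month measure in 12.4 is a brushing measure.

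**The concern.** The exit interview belongs to the outreach center visit at which the skill is taught. A patient asked there how often she flosses now can report only an existing habit, an intention, or what she thinks the interviewer hopes to hear. She has had no days at home in which to change. The study does contact her again about a month later, when the answer would mean something, but by the protocol's description it then asks about fluoride toothpaste and brushing.

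At stake is what the study can pass on to the larger randomized trial that it is meant to inform. Brushing has a 1-month measure. Flossing, the other behaviour row in Table 3, has none described, and no reason is given. A within-patient flossing change from intake to 1 month could not be constructed, because neither form is described as holding a frequency item.

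**Working it through.** **1. The plan's own figures.** Table 3, flossing row:
- Absolute change in the prior project: 22.1 − 4.4 = 17.7 points, listed as an expected +20.
- Relative change: 17.7 / 4.4 = 402%, listed as +400%.
- At a 4.4% baseline, +20 points would be 20 / 4.4 = 455%, and +400% would be 4 × 4.4 = 17.6 points. These are rounded expectations, and the point does not turn on the difference.

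**2. Where flossing is measured, by contact.**

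| Contact | Floss use | Floss frequency | Time to practise |
|---|---|---|---|
| Intake survey (7.2) | yes, one option in a list | no | none (baseline) |
| Exit interview (7.2, 12.4) | – | yes, recalled before and present | none; center visit |
| 1-month contact (7.3) | not named | not named | about 1 month (−7 days to +1 month) |

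That the exit interview falls on the day of the demonstration is inferred from three places: 7.2 lists it with the outreach center activities, the Protocol Summary gives one in-person visit, and 7.3 times the follow-up after the intervention. The other later sources do not fill the gap. The EHR and outside dental providers are described for dental visits (12.4), and the community health worker logs for activities and communications (6.2).

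**3. Would the planned number support the missing comparison?** The documents give no alpha, power or sample size calculation (12.2), so the following is illustrative.

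Inputs: n = 90 (5.1), or 54 if only 60% of the 90 gave both answers (assumed); two-sided alpha 0.05 (assumed); true net change d = 0.20 (Table 3). The share moving the opposite way, q, runs from 0 to 0.044 (assumed; the upper end is the prior project's 4.4% baseline). The share changing in either direction is s = 0.20 + 2q.

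95% half-width of the paired change = 1.96 × √[(s − d²)/n]:
- n = 90, q = 0: 1.96 × √(0.160/90) = 8.3 points
- n = 90, q = 0.044: 1.96 × √(0.248/90) = 10.3 points
- n = 54, q = 0: 1.96 × √(0.160/54) = 10.7 points
- n = 54, q = 0.044: 1.96 × √(0.248/54) = 13.3 points

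McNemar power (normal approximation) = Φ{[d√n − 1.96√s] / √(s − d²)}:
- n = 90: 99% (q = 0), 96% (q = 0.044)
- n = 54: 93% (q = 0), 80% (q = 0.044)

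These use the change within each patient. They need the prior project's baseline only to bound q, and a larger q would widen the intervals. On these assumptions what is missing is the question, not the patients.

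**The case against.** The strongest reply is that Table 3 has its instrument. Section 12.4 ties the table to the exit interview, which follows the demonstration and asks flossing frequency for both before and now. A reader might infer from this point that no flossing frequency is collected after the demonstration at all. The documents do not support that: each interviewed patient gives one. What stands is narrower, namely that a same-day answer says nothing about practice at home.

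A second reply is that the content of the 1-month form is inferred. The form is not in the text, 7.3 opens with the broader term of dental hygiene behaviors, and its description is evidently incomplete: it omits the 2-minute and soft-bristle elements that 12.4 requires at 1 month. So it would be too strong to state as fact that the form leaves flossing out. If the form merely carried over the intake floss option, though, it would still record use and not frequency.

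Third, the timing weakness also affects the present-time brushing answer in the exit interview. That is true, but brushing is asked about again at 1 month, and flossing is not described as being.

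Finally, flossing is peripheral. The primary outcome is patient satisfaction (3.2.1), and no success threshold in 7.2, 12.2 or 12.4 uses flossing. Keeping follow-up to the central behaviour is defensible in an uncontrolled feasibility study. This limits the weight of the point but does not remove it, because the plan itself states a flossing hypothesis.

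**Conclusion.** The point holds in limited form. Following the plan as described, the +20-point flossing expectation would be assessed only from two answers given at one sitting, and there would be no flossing frequency after a period at home for any of the roughly 90 interview patients. This rests on two readings: that the exit interview takes place at the demonstration visit, and that 7.3 fairly describes the 1-month form on this item.

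It would be wrong to go further and conclude that a study objective or success criterion fails. It would also be wrong to treat a 1-month percentage lying above 4.4% as evidence of change: that baseline comes from another community, and the Table 3 footnote allows that the Chinese American baseline may be very different. The patient's own intake answer is the right comparator. This is a minor to moderate improvement.

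**What to change.** Add the Table 3 flossing-frequency question, with the response categories used in the exit interview, to the intake Oral Health Survey (7.2) and to the modified survey at the 1-month contact (7.3). In 12.4, state that the flossing row is assessed on the within-patient change from intake to 1 month, reported with a paired confidence interval and the number of patients giving both answers. Keep the exit-interview answers as supportive. The item must be in place before the first intake, since a missed baseline cannot be recovered.

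If the investigators prefer not to add it, 12.4 should say that the flossing expectation concerns same-visit self-report only. If the 1-month form already asks flossing frequency, 7.3 should say so; the intake item and the 12.4 sentence would still be needed.

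The cost is one question on two existing forms and a sentence in each of three sections, with no new contact, staff or patients. The downsides are slightly more respondent time, loss of patients not reached at 1 month, and possibly a smaller observed change than +20 points. The documents do not say how long after its demonstrations the prior project asked its question, so its 17.7 points may not carry over to 1 month of home practice.
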